### 9.1.1 Background and rationale

Oncologic imaging is in the midst of a paradigm shift in which a number of advanced quantitative techniques reporting on tissue function and composition at the molecular level are now being advanced as candidate biomarkers for cancer detection, characterization, and treatment response assessment. This advanced imaging correlative deploys several promising MRI techniques within a single multiparametric MRI examination. The overall hypothesis for the advanced imaging correlative is that these techniques, either individually or in combination, can provide clinically useful information beyond that provided by standard-of-care imaging in the context of metastatic TNBC. The components of the multiparametric MRI examination, and hypotheses related to these components, are outlined briefly below:

- **Dynamic contrast enhancement MRI (DCE-MRI)** is a method for characterizing tissue vascularity. The technique involves rapid acquisition of serial MR images before, during, and after injection of an intravenous contrast agent; these images are then analyzed with mathematical models to estimate quantitative values for pharmacokinetic and tissue properties. We hypothesize that early changes in these derived DCE-MRI parameters (i.e., from baseline to day 14-21) will predict treatment response. We will also test whether baseline DCE-MRI parameters by themselves predict patient response to treatment, whether baseline DCE-MRI parameters can discriminate between AR+ and AR- subtypes of TNBC, and whether DCE-MRI parameters at the time of progression are significantly different from DCE-MRI parameters at baseline and early during therapy. Finally, we will evaluate the correlation between DCE-MRI parameters and phosphorylated p-ERK1/2, p-S6, and p-AKT S-473 levels at serial core biopsies.
- **Diffusion-weighted MRI (DW-MRI)** is a method for quantifying tissue cellularity. The technique reports on the ability of water molecules to move randomly, or diffuse, within tissue; more cellular tissues tend to have more barriers to water movement and, therefore,

restricted water diffusion when measured by MRI. We hypothesize that early changes in quantitative DW-MRI parameters will predict treatment response. We will also test whether baseline DW-MRI parameters by themselves predict patient response to treatment, whether baseline DW-MRI parameters can discriminate between AR+ and AR- subtypes of TNBC, and whether DW-MRI parameters at the time of progression are significantly different from DW-MRI parameters at baseline and early during therapy. Finally, we will evaluate the correlation between DW-MRI parameters and phosphorylated p-ERK1/2, p-S6, and p-AKT S-473 levels at serial core biopsies.

- **Chemical exchange saturation transfer (CEST) MRI.** CEST is a method for the detection and characterization of specific low-concentration metabolites in tissue. Recent attention has focused on amide proton transfer (APT), a form of CEST reporting on amide groups in proteins and peptides, as a novel cancer imaging biomarker. The technique exploits the base-catalyzed chemical exchange between amide protons and water molecules and is sensitive to both protein concentration and pH. We hypothesize that early changes in quantitative APT will predict treatment response. We will also test whether baseline APT measurements can by themselves predict patient response to treatment, whether baseline APT measurements can discriminate between AR+ and AR- subtypes of TNBC, and whether APT measurements at the time of progression are significantly different from APT measurements at baseline and early during therapy. Finally, we will evaluate the correlation between APT measurements and phosphorylated p-ERK1/2, p-S6, and p-AKT S-473 levels at serial core biopsies.
- **Multiparametric MRI** is itself an imaging technique under intensive investigation. We hypothesize that tumor characterization may be even further improved by combining information derived from a number of quantitative imaging techniques to assemble a multifaceted, multidimensional construct of tumor phenotype and behavior. We will test different permutations of quantitative DCE-MRI, DW-MRI, and CEST parameters for detecting lesions, characterizing lesions, and monitoring response to treatment in the study population.

### 9.1.2 Participant selection: MRI Advanced Imaging Correlative

#### 9.1.2.1 Inclusion criteria

- Patients must be enrolled at Vanderbilt University Medical Center.
- Patients must have planned core biopsies from one of the following sites: breast/axilla, lower neck/supraclavicular region, liver, or pelvic bone marrow.
- Patients must have measureable disease at the site selected for core biopsies. Measureable disease is defined as presence of at least one lesion measuring greater than 10 mm in long axis diameter.

#### 9.1.2.2 Exclusion criteria

- Patients with inadequate renal function (creatinine  $\geq 1.5$  times upper limit of normal) or acute or chronic renal insufficiency (glomerular filtration rate  $< 30$  mL/min).

- Patients who have any type of bioimplant activated by mechanical, electronic, or magnetic means (e.g., cochlear implants, pacemakers, neurostimulators, biostimulators, electronic infusion pumps, etc), because such devices may be displaced or malfunction.
- Patients who have any type of ferromagnetic bioimplant that could potentially be displaced.
- Patients who have cerebral aneurysm clips.
- Patients who may have shrapnel imbedded in their bodies (such as from war wounds), metal workers and machinists (potential for metallic fragments in or near the eyes).
- Patients who have exhibited past allergic or other adverse reactions in response to intravenous injection of Magnevist® (gadopentetate dimeglumine) or other gadolinium-containing contrast agents.
- Patients who exhibit noticeable anxiety and/or claustrophobia or who exhibit severe vertigo when they are moved into the magnet bore.
- Patients incapable of giving informed written consent, for the following reasons:
  - Inability to adhere to the experimental protocols for any reason
  - Inability to communicate with the research team
  - Limited ability to give informed consent due to mental disability, altered mental status, confusion, or psychiatric disorders
  - Prisoners or other individuals deemed to be susceptible to coercion

### 9.1.3 MRI Imaging procedures

Patients will undergo multiparametric MRI at baseline, at day 14-21, and at the end of treatment. The multiparametric MRI examinations should be scheduled to coincide with the planned core biopsies as much as is reasonably practical. At any given timepoint, however, **every effort should be made to complete the MRI examination before the core biopsy**, because hemorrhage from the core biopsy may interfere with the MRI measurements.

The general scan order and anticipated scan durations are summarized below:

1. Scout images, transmitter tuning, shimming, slice prescription – 5 min
2.  $T_1$  map – 2.5 min
3. Diffusion-weighted MRI (DW-MRI) – 5 min
4. Chemical exchange saturation transfer (CEST-MRI) – 10 min
5. Pre-contrast  $T_1$ -weighted anatomic MRI – 2 min
6. Dynamic contrast-enhanced MRI (DCE-MRI) – 8 min  
\*Intravenous injection of the FDA-approved contrast agent (CA) Magnevist® (gadopentetate dimeglumine, 0.1 mmol/kg) 60 sec after the start of the scan. Infusion time is 5-10 sec, depending on patient weight. CA will be followed by saline flush.
7. Post-contrast  $T_1$ - and  $T_2$ -weighted anatomic MRI – 10 min

## 9.2 Tissue Samples (All participating sites)

### 9.2.1 AR testing

Please see Section 5 for AR testing and requirements for tissue for AR testing.

### 9.2.2 Archival tissue

Once a patient is confirmed to be AR positive, meets all eligibility requirements, and is registering for the study, formalin-fixed paraffin embedded tissue blocks from the patient's primary tumor or metastatic lesion collected for diagnostic and therapeutic purposes is requested. Blocks will be returned within 8 weeks (or earlier if requested); tissue taken from these blocks will not be returned.

In case the participating institutions are not allowed to release clinical paraffin embedded blocks, ideally we will need the following cut in this order:

1. H&E slide
2. 5 peels cut at 10  $\mu$ m each in a single DNase-free/RNase-free tube
3. H&E slide
4. 3 peels cut at 10  $\mu$ m each in a single DNase-free/RNase-free tube
5. H&E slide
6. 10 unstained slides cut at 5  $\mu$ m each on charged slides
7. H&E slide

If remaining tissue is insufficient for the complete request, please send:

1. H&E slide
2. 3 peels cut at 10  $\mu$ m each in a single DNase-free/RNase-free tube
3. H&E slide
4. 2 peels cut at 10  $\mu$ m each in a single DNase-free/RNase-free tube
5. H&E slide

If remaining tissue is limited, please send:

1. H&E slide
2. 2 peels cut at 10  $\mu$ m placed in a single DNase-free/RNase-free tube
3. H&E slide

After removing all stray tissue from the area, the microtome blade and surrounding area should be wiped with 70% ETOH before starting to section the block and between patients to prevent contamination with extraneous tissue.

**All formalin-fixed paraffin embedded tissue and/or slides should be sent with a cold pack to avoid melting that could damage tissue analysis.**

### 9.2.3 Fresh biopsy of metastatic site

Once a patient is confirmed to be AR positive, meets all other eligibility, and registers for the study, collection of tissue from a metastatic site, if reasonably safe, is also a requirement for entry to this study. A biopsy can also be used for AR testing for the study (see Section 5). Pre-trial and day 14-21 biopsies should be collected. Research tissue blocks prepared from

these metastatic biopsies will not be returned. **All patients must have a biopsy of a metastatic site at the end of treatment if the patient is removed for disease progression or is on the enzalutamide only arm and crossing over to enzalutamide + taselisib. See section 9.2.4 below for details on collecting tissue.**

#### 9.2.4 Guidelines for Tissue Acquisition on Biopsies of Metastatic Lesions

Tissue specimens, when feasible, will be collected from recurrent or metastatic lesions using standard institutional procedures. The amount of tissue collected will follow the guidelines listed below. If a patient has more than one site of disease, only one site needs to be biopsied, and the site is left to the discretion of the patient and the treating physician. If a patient is undergoing resection of a lesion for clinical reasons (i.e. wedge resection of a new lung lesion for confirmation of diagnosis or re-testing of hormone receptor or HER2 status; or, resection of a chest wall lesion; or, resection of a lymph node), then the patient may opt to have a portion of that tissue (roughly equivalent to the goal amount of tissue listed in the guidelines above, i.e. the equivalent of two 5-mm punch biopsies of the skin, or 3-6 18-gauge core biopsies) stored for research at the time of the procedure.

Listed below are the goal amounts of tissue for patients who undergo core biopsy or punch biopsy, or who have either ascites fluid or pleural fluid accessible for collection. Please note that the below are guidelines for the amount of tissue to be obtained at the baseline biopsy, and are not meant to replace clinical judgment at the time the procedure is performed. Less than the goal quantity of tissue is accepted for each type of biopsy, and will be left to the clinical judgment of the physician performing the procedure.

- Breast: A goal of 3-6 core biopsy specimens will be obtained using standard institutional guidelines for a diagnostic core biopsy of a breast mass
- Skin/chest wall: A goal of one to two 5-mm punch biopsies
- Lymph node: A goal of 3-6 core biopsy specimens will be obtained using an 18-gauge needle
- Liver: A goal of 3-6 core biopsy specimens will be obtained using an 18-gauge needle
- Lung: A goal of 3 core biopsy specimens will be obtained using an 18-gauge needle. Due to the risk of pneumothorax associated with core needle biopsies of lung nodules, peripheral lesions should be carefully selected.
- Bone: Because the yield of malignant tissue from bone biopsies tends to be relatively low, if a patient has another accessible site of disease (i.e. skin, lymph node, liver), that site should be biopsied preferentially. If bone is the only biopsy-accessible site, then a goal of 3-6 core biopsy specimens will be obtained using an 18-gauge needle.
- Pleural Fluid (known to be due to malignancy): A goal of 500 cc of pleural fluid will be obtained with a standard thoracentesis procedure, with or without image guidance, according to the clinical judgment of the treating physician and clinician performing the procedure. Less than the goal amount is acceptable, and should be based upon the clinical judgment of the Investigator and the clinician performing the procedure. If more than the goal amount of fluid is obtained, then the entire specimen (with the exception of what is needed for clinical purposes, if applicable) will be stored at Vanderbilt.

- Ascites fluid: A goal of 500 cc of ascites fluid will be obtained with a standard paracentesis procedure, with or without image guidance, according to the clinical judgment of the treating physician and clinician performing the procedure. Less than the goal amount is acceptable, and should be based upon the clinical judgment of the Investigator and the clinician performing the procedure. If more than the goal amount of fluid is obtained, then the entire specimen (with the exception of what is needed for clinical purposes, if applicable) will be stored at Vanderbilt.

#### 9.2.5 Instructions on fresh tissue specimen handling

##### 1) Core biopsy specimens

\*Tissue obtained at Vanderbilt will be handled differently as it does not need to be shipped. Please see the Vanderbilt lab manual for handling if obtaining a biopsy at Vanderbilt\*

- First core biopsy should be suspended in 10% buffered formalin.
- Second core biopsy should be suspended in “RNAlater” solution\*
- Third core biopsy should be suspended in “RNAlater” solution\*
- Fourth core biopsy should be suspended in 10% buffered formalin.
- Fifth core biopsy should be suspended in “RNAlater” solution\* (outside sites)
- Fifth core biopsy should be placed in cell culture media (Vanderbilt only)
- Sixth core biopsy should be suspended in 10% buffered formalin

If only 2 core biopsies are obtained, one should be placed in “RNAlater solution”\* and the other should be suspended in 10% buffered formalin.

\*RNAlater kits will be provided. 1 core should be placed in one 1.5ml specimen tube. All samples should be shipped immediately, according to the lab manual.

##### 2) Resected lesion (chest wall, lymph node, etc).

- For specimens greater than 5mm, the specimen should be bisected and one half placed in RNA later and the other in 10% buffered formalin

##### 3) Fine needle aspiration (FNA)

For patients in whom a core biopsy is not possible and who thus undergo fine needle aspiration (FNA), 3 passes should be collected.

- First pass should be evacuated and rinsed directly into 10% buffered formalin
- Second pass should be evacuated and rinsed directly into 5-10 volumes “RNAlater” solution
- Last pass should be evacuated and rinsed directly into 10% buffered formalin

### 9.3 Blood/plasma collection (All Participating Sites)

Streck Cell-Free DNA BCT kits will be provided for circulating tumor DNA. One vial of whole blood should be collected in a Cell-Free DNA BCT tube (Streck tube). Fill the tube completely. Remove the tube from the adapter and immediately mix by gentle inversion 8 to 10 times. Collection times are: cycle 1/day 8, cycle 2/day 15, and end-of-treatment (also cycle 1/day 1 for those crossing over to enzalutamide + taselisib - see study calendar).

Tube should be packed according to the lab manual and sent immediately (within 24 hours) to VICC at the address below with a tissue/blood registration form. **Do not freeze specimens collected in Streck tube.**

### 9.4 Tissue specimen and blood/plasma labeling and documentation

Label each collection containers with Patient ID sequence number/code letter, site and location of biopsy, date and time.

If sample comes in contact with contaminate, make note in information section of paperwork.

Enter time core biopsy was collected on paperwork.

If not retrieved on site by VICC CTSR personnel, outside sites should ship specimens along with Tissue Registration Form directly to:

The specimens will be logged in as a consented specimen and available for molecular pathology studies.

Ship ALL samples with a cold pack. If specimens are obtained on a Friday or holiday weekend, they should be refrigerated (not frozen) and sent out the following week.

**\*\*Specimens should be mailed to arrive at VUMC from Monday 8AM through Friday 1PM\*\***

### 9.5 Pharmacokinetic Sampling

Pharmacokinetic sampling will occur in the phase Ib portion and in 10 patients in the phase II portion (phase II at Vanderbilt only). PKs for patients in the phase Ib portion: will be obtained on cycle 1, day 8 at: 0-4 hours prior to dose of taselisib and 1, 3, and 6 hours post administration taselisib; on cycle 2, day 15 at: 0-4 hours prior to dose of taselisib and enzalutamide and 1, 3, and 6 hours post administration taselisib and enzalutamide; on cycle 4, day 1, plasma sample should be obtained 0-4 hours before taselisib and enzalutamide administration, and 3 hours post-administration of both drugs.

The first ten subjects on the enzalutamide + taselisib arm at Vanderbilt should initiate taselisib on day 1 and enzalutamide on day 9 to facilitate PKs, which will be done on the first 10 Vanderbilt patients on the combination arm only. PKs in phase II (Vanderbilt only) should be obtained on patients receiving both enzalutamide and taselisib on C1D8, C2D15, and C4D1 at 0-4 hours prior to taselisib and enzalutamide and 2 to 4 hours post treatment. Please see the lab manual for details of collection and for information about shipping the samples.

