**STUDY CALENDAR: ENZALUTAMIDE +/- TASELISIB**

Evaluation a	Screening b Day-28 – Day 1	Daily	Treatment period								Every 2 cycles from CID1	Post treatment		
			Cycle 1 (28-days)		Cycle 2 (28-days) c			Additional cycles c	Cycle 4	End-of- treatment d		30 day follow-up d		
			Day 1	Day 15	Day 1	Day 8 t	Day 15	Day 1	Day 1					
Informed consent	X													
Inclusion/exclusion criteria	X													
Brain imaging (MRI or CT scan) e	X													
Demographics/ medical history	X													
Physical exam/signs & symptoms b,f	X		X	X	X	X	X	X	X			X		
Vital signs (including oxygen sat)	X		X	X	X	X	X	X	X			X		
12-lead ECG g	X													
ECOG Performance Status	X		X	X	X	X	X	X	X			X		
Blood collection	Clinical laboratory tests h	X		X	X	X	X	X	X			X		
	Fasting plasma glucose i	X		X	X	X	X		X			X		
	Pregnancy test j	X												
	HbA1C	X												
	PT (or INR)/PTT	X												
	PK assessments k					X		X		X				
	Circulating tumor DNA					X		X				X		
Tumor assessment CTs, bone scan l	X									X				
Archived tumor blocks/slides m	X													
Tumor biopsy (metastatic site) n	X						Day 14-21				X			
Imaging Correlate: CEST-MRI o	X						Day 14-21				X			
Enzalutamide administration (oral) p		X	Oral, once-daily administration											
Taselisib administration (oral): if on taselisib arm		X			Oral, once-daily administration, starting cycle 2, day 1									

Evaluation a	Screening b	Treatment period								Every 2 cycles from C1D1	Post treatment	
		Daily	Cycle 1 (28-days)		Cycle 2 (28-days) c			Additional cycles c	Cycle 4		End-of-treatment d	30 day follow-up d
	Day 1		Day 15	Day 1	Day 8 t	Day 15	Day 1	Day 1				
Pill Diary a		X										
Concomitant medications f	X		X	X	X	X	X	X				
Adverse events	X		X	X	X	X	X	X				X
Biopsy questionnaire g								X				

AE = adverse event; BSA = body surface area; CX = Cycle X, where X is the cycle number; DLT = dose-limiting toxicity; ECG = electrocardiogram; ECOG = Eastern Cooperative Oncology Group; HbA1C = glycosylated hemoglobin; IMP = investigational medicinal product; INR = international normalized ratio; PT = prothrombin time; PTT = partial prothrombin time; SAE = serious adverse event

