- l Tumor assessment should be performed approximately every 2 cycles (up to -5 days) while on study treatment and at End-of-treatment visit if not obtained within the past 6 weeks. Scans should consist of CT scan of the chest, abdomen, and pelvis and a bone scan at baseline. Subsequent scans should consist of CT chest, abdomen and pelvis, and bone scan if bone metastases were present on the baseline studies. At the end of treatment, all scans (baseline and through disease progression) should be sent on a CD to the Vanderbilt Cancer Imaging Support Laboratory for central review and assessment. See Section 10.5 for details and address.
- m Archived tumor biopsy specimen: 20 unstained slides of archived biopsy block (unstained slides) or fresh tumor biopsy will be requested at the time of enrollment prior to initiation of treatment.
- n Tumor biopsies will only be performed in the phase II portion. A tumor biopsy from a metastatic site will be obtained from patients prior to day 1, at cycle 2 day 14-21, and upon progression of disease. The third biopsy (at the end of treatment) will not be required for patients who are removed from study for reasons other than disease progression. A patient who undergoes a research biopsy procedure for the purpose of this protocol, and in whom inadequate tissue is obtained, is not obligated to undergo a repeat biopsy.
- o See section 9.1. Required only for patients at Vanderbilt and only in the phase II portion. This should be performed prior to tumor biopsy, if possible. If MRI sub-study is not feasible due to scheduling, MRI weight limits, etc., patients may still continue with the remainder of the study.
- p Subjects on the enzalutamide + taselisib arm should begin enzalutamide on day 1 of cycle 1, and taselisib on day 1 of cycle 2.
- q Pill Diary can be found in the packet of supplemental forms.
- r See Section 6.4.2.
- s Phase II only. Biopsy questionnaire should be filled out by the patient on C3D1. Form can be found in the packet of supplemental forms.
- t The cycle 2 day 8 visit is only needed for patients on the combination of taselisib + enzalutamide. Patients on enzalutamide only do not need a visit on this day.

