### 6.3.1 Taselisib

Taselisib tablets are administered once daily until disease progression or intolerable toxicity. Taselisib administration will begin on C2D1 for patients enrolled on the combination arm (with enzalutamide alone beginning on C1D1). Each dose should be taken with a minimum of 3–4 ounces (90–120 mL) of water with or without food in the morning (before noon). If a dose is missed (not taken by noon), the patient will resume dosing with the next scheduled dose. Missed or vomited doses will not be made up. The occurrence and frequency of any vomiting during a treatment cycle must be noted as an adverse event. Patients should swallow the capsules as a whole and not chew or crush them.

A sufficient number of taselisib tablets should be provided to the patient to last until the next cycle. Patients will be instructed to bring their bottles of study drug and their medication diary with them to each study visit.

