### 6.3.2 Enzalutamide

The daily dose of enzalutamide is 160 mg/day given in 4 capsules (40 mg each) by mouth. Enzalutamide capsules are administered once daily until disease progression or intolerable toxicity. The first ten subjects on the enzalutamide + taselisib arm at Vanderbilt will have blood draws for PKs as outlined in the study calendar.

Patients should be instructed to take the dose of enzalutamide at the same time in the morning (before noon) every day, with or without food. Enzalutamide should be taken with a glass of water. Patients should swallow the capsules as a whole and not chew, crush, or open them.

If the patient forgets to take her/his dose and it is past noon, then the dose should be withheld that day and enzalutamide should be restarted the following day. Missed or vomited doses will not be made up. The occurrence and frequency of any vomiting during a treatment cycle must be noted as an adverse event.

A sufficient number of enzalutamide capsules should be provided to the patient to last until the next visit or, at the investigator's discretion, to last until the next cycle. Patients will be instructed to bring their bottles of study drug and their medication diary with them to each study visit.

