#### 7.2.1.3 *Dermatological Toxicity*

Treatment-related rash, including cases of Grade 3 rash, has occurred in patients who received taselisib. This rash is commonly manifested as maculo-papular with or without pruritus. Incidence rate and severity of rash appear to be dose dependent. The rash has resolved upon holding of taselisib and/or supportive therapy (e.g., topical or systemic steroids). Rash and other dermatological events should be closely monitored, and patients with severe rash should be monitored for associated signs and symptoms such as fever and hypotension that may be suggestive of a systemic hypersensitivity reaction. For severe rash, dosing of taselisib should be interrupted, and patients should be treated with supportive therapy per standard of care. Use of topical antihistamine, as well as topical or systemic corticosteroids, may be considered. Dose delay and modification guidelines for patients who experience rash are outlined in Table 3. Of note, no grade 3 or 4 rashes were noted in the phase Ib portion of this study with dose escalation to 8 mg taselisib. However, in the phase II portion with taselisib at 4 mg, 7 of 8 patients on the combination arm experienced a grade 3 or 4 rash with fever within the first 14 days of treatment. No patients who crossed over from enzalutamide to taselisib + enzalutamide experienced the rash, thus the study is amended so that all patients have a 28 day lead-in with enzalutamide prior to starting taselisib (similar to the cross-over arm). The rash resolved in all patients with IV steroids, antihistamines and supportive care.

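### Section 9.5 still orders taselisib first for ten Vanderbilt combination-arm patients, contradicting the 28-day enzalutamide lead-in, and lists a phase II PK day (C1D8) that footnote k does not

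*Combined protocol and SAP*

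**What the plan says.** Section 9.5 (Pharmacokinetic Sampling) directs: "The first ten subjects on the enzalutamide + taselisib arm at Vanderbilt should initiate taselisib on day 1 and enzalutamide on day 9". The reason it gives is to make the PK work easier. It then sets phase II PK sampling at C1D8, C2D15 and C4D1.

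The other current phase II dosing text gives the opposite order:

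- Section 7.2.1.3 reports that "7 of 8 patients on the combination arm experienced a grade 3 or 4 rash with fever within the first 14 days of treatment" and that "No patients who crossed over from enzalutamide to taselisib + enzalutamide experienced the rash". It concludes: "thus the study is amended so that all patients have a 28 day lead-in with enzalutamide prior to starting taselisib".
- The taselisib row of the main study calendar reads "Oral, once-daily administration, starting cycle 2, day 1".
- Calendar footnote p reads "Subjects on the enzalutamide + taselisib arm should begin enzalutamide on day 1 of cycle 1, and taselisib on day 1 of cycle 2".
- Section 6.3.1 likewise starts taselisib at C2D1, after a first cycle of enzalutamide alone.

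On PK timing, calendar footnote k puts the phase II samples at C2D1, C2D15 and C4D1. Section 6.3.2 says: "The first ten subjects on the enzalutamide + taselisib arm at Vanderbilt will have blood draws for PKs as outlined in the study calendar".

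**The concern.** The lead-in is a safety measure adopted during the trial. It makes combination-arm patients resemble the crossover patients, who were already on enzalutamide when taselisib was added and did not get the rash. Section 9.5 withholds it from a named group at the coordinating site. The sentence is phrased as a direction to be carried out, and it carries its own rationale. A study coordinator could therefore reasonably take it for a deliberate PK exception rather than text left over from before the amendment.

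Any PK patient dosed that way would start taselisib with no enzalutamide beforehand. The PK-day mismatch matters less. Under the lead-in, a C1D8 sample is drawn before any taselisib has been given, so it cannot inform the taselisib part of the PK objective in Section 2.2.

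**Working it through.** No sample-size or error-rate figure bears on this point. The check is a comparison of start days and sampling days.

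**Inputs.** Cycle length is 28 days (Section 6.2.1), so C1D8 is day 8 and C2D1 is day 29. The lead-in start days come from footnote p and Section 6.3.1. The competing start days come from Section 9.5.

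| | Lead-in (7.2.1.3, calendar, 6.3.1) | Section 9.5 |
|---|---|---|
| First enzalutamide dose | day 1 | day 9 |
| First taselisib dose | day 29 | day 1 |
| Enzalutamide days before taselisib | 29 − 1 = 28 | 0 |
| Taselisib days before enzalutamide | 0 | 9 − 1 = 8 |

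**Shift in start dates under Section 9.5.** Taselisib begins 29 − 1 = 28 days earlier. Enzalutamide begins 9 − 1 = 8 days later.

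**PK days.** Section 9.5 has {C1D8, C2D15, C4D1} and footnote k has {C2D1, C2D15, C4D1}. One of three differs. Under the lead-in, C1D8 falls 29 − 8 = 21 days before the first taselisib dose. The calendar has no C1D8 column.

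**Does any other text settle the order?**

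1. The lead-in in Section 7.2.1.3 covers every patient. The calendar row, footnote p and Section 6.3.1 cover the whole combination arm. None carves out Vanderbilt or PK patients.
2. Section 6.3.2 sends the first ten Vanderbilt patients to the calendar, but only for blood draws. It does not address which drug starts first.
3. No stated rule says which section prevails if they conflict.
4. Section 6.2.1 describes the same taselisib-first order in the past tense, so it can be read as history. Section 9.5 is worded as a direction and cannot.

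**How many patients could be affected?** The documents do not say how many of the ten PK places were filled, so the range is 0 to 10. Assume that the 8 patients mentioned in Section 7.2.1.3 were the whole phase II combination-arm accrual when the lead-in was adopted. Then at most 8 places had been used, and between 10 − 8 = 2 and 10 − 0 = 10 were still open.

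**The case against.** The best reply is that the intended order is clear and Section 9.5 is simply stale. Section 6.3 names 6.3.1 and 6.3.2 as the sections on drug administration. Section 9.5 sits in the correlative-studies chapter. Section 7.2.1.3 says outright that the study was amended. Section 6.5 points to the calendar for assessments during treatment, which largely settles the PK days. At most ten patients at one site are involved, and Section 12.3 provides for continuous monitoring by the Protocol Chair and the Vanderbilt research team.

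The safety inference is also limited. Section 7.2.1.3 does not say which start order the 7 affected patients followed or how many were treated at Vanderbilt. By Section 6.2.1, Vanderbilt combination patients in phase Ib also took taselisib first, yet no grade 3–4 rash was seen in phase Ib with escalation to 8 mg.

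Much of this stands. The lead-in is very probably what the sponsor intends, causation is not shown, exposure could be zero, and no loss of monitoring is demonstrated. C1D8 was a usable taselisib-alone sample under the old order, although on that day the patient was not yet taking both drugs, as the Section 9.5 PK sentence presumes.

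None of it removes the conflict. Agreement among several general statements does not clearly override a specific instruction for a subgroup singled out for a stated purpose. A safety-driven start order should not depend on the reader guessing which section is out of date.

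**Conclusion.** The concern holds. Section 9.5 contains a current dosing instruction that is incompatible with the lead-in in Section 7.2.1.3, the calendar and Section 6.3.1. For any patient dosed under it, enzalutamide exposure before taselisib falls from 28 days to 0. The number of such patients is unknown (0 to 10, or 2 to 10 open places at adoption of the lead-in under the accrual assumption above).

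The dosing sentence alone makes this a correction that must be made. The C1D8 against C2D1 mismatch is secondary. The conclusion does not depend on taselisib-first dosing having caused the rash. It depends on the sponsor having required the lead-in for every patient while leaving one instruction that withholds it. Sample size, error rates and the primary analysis are unchanged.

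**What to change.** In the phase II paragraph of Section 9.5:

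- Replace the start order with enzalutamide from C1D1 and taselisib from C2D1.
- Change the phase II PK days to C2D1, C2D15 and C4D1, matching footnote k.

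Optional tidying in the same amendment: bring the cycle 1, day 8 ctDNA collection in Section 9.3 into line with the calendar, and mark the Section 6.2.1 statement covering both phases as historical.

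The cost is a wording change. The phase II taselisib-alone PK sample is lost, but the lead-in already rules it out, and the phase Ib C1D8 samples remain. The C2D1 pre-dose sample will contain no taselisib, because that day is the first taselisib dose. The PK analysis should treat it accordingly.
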